## 6 STUDY INTERVENTION(S) OR EXPERIMENTAL MANIPULATION(S)

### 6.1 STUDY INTERVENTION(S) OR EXPERIMENTAL MANIPULATION(S) ADMINISTRATION

All participants will receive a Fitbit® for the collection of sleep and activity (steps) data, and will download the Fitbit® app and study app, CareQOL, on their personal mobile device (iOS or Android). The CareQOL app will deliver ecological momentary assessments (EMAs) once per day, compile and display data (including that collected on the Fitbit®), and deliver study notifications, including messages for the participant to complete the daily EMA and other study surveys as well as delivering the personalized study intervention prompts to the intervention group (Just-in-time adaptive intervention [JITAI] group).

All study participants will complete 3 EMA questions daily on the CareQOL app. Each participant will be prompted by a push notification in a five-hour window (based on participant preference) from the app to answer the questions. The EMA questions are comprised of: 1 question on caregiver strain (taken from the CareQOL Caregiver Strain item bank), 1 question on anxiety (taken from the PROMIS Anxiety

item bank) and 1 question on depression (taken from the PROMIS Depression item bank). Questions are on a five-point scale, with higher scores indicating more of the named construct.

In addition to the collection of the EMA data, the app complies and displays a graphical summary of historical data for caregiver stress (strain), worry (anxiety), sadness (depression), steps (collected by the Fitbit®) and hours of sleep (collected by the Fitbit®) on a participant dashboard. Participants can view this information for the past week, past month or past year. This is available to all participants as a pull – that is, it is available at all times but is accessed only if the user chooses to access it.

In this study, half of the participants will be randomized to receive the intervention (JITAI; described below); the remaining participants will be in the control group, who will not receive the JITAI but will complete the activities already described in this section. Participants who are randomized to receive the JITAI will have a 50/50 chance of receiving the intervention each day.

The JITAI aims to promote behavioral change through motivational messages that are delivered through the CareQOL app as push notifications. These notifications provide a trigger for participants to initiate or continue behavior change and/or monitor behaviors (through engagement with the app). The push notifications are low burden: participants can personalize the administration time (in a 5-hour window) and notifications can be viewed quickly on their phone's lock screen. Participants can also choose not to engage with the notification at the time it is sent if it is inconvenient – they can return to it later if needed.

The JITAI push notifications are aimed at promoting healthy behaviors (physical activity and good sleep hygiene) and improving mood (anxiety, depression, caregiver strain). If receiving a notification, the message will be randomly drawn from this pool of messages. Some messages will use participants' data directly in the messages (e.g., You walked an average of 8,120 steps this week), and most of messages will be personalized based on data (e.g., someone with low steps will get a different message than someone with medium steps than someone with high steps; high-medium-low). Messages are comprised of one or more of the following different types: 1) Data feedback; 2) Facts; 3) Tips; and 4) Support. Randomization of the days the participants receive messages and the message the participant receives from the pool will be done through the CareQOL app.

The study intervention period is 90 days (3 months); in addition, there is an ~10-day run-in period where participants will install/adjust/troubleshoot the study technology and the app will gather baseline data to use to tailor messages once the intervention period begins.

## 6.2 FIDELITY

For this study, the intervention will be administered via the CareQOL app. The study team will conduct training during the baseline visit with each participant which will include:

- Helping the participant download and register for the CareQOL and Fitbit® apps on their personal device
- Helping the participant set any relevant app settings (e.g., make sure alerts are turned on/off, privacy settings, etc.)
- Demonstrating the CareQOL app features to the participant (e.g., participant dashboard, etc.)

- Ensuring that the participant understands the importance of entering the daily ratings and wearing the Fitbit®
- Explaining the relationship between the daily ratings and Fitbit® data and the intervention prompts (JITAI group only)
- Demonstrating how to sync the Fitbit® (including using the Fitbit® app) and how to enter the daily ratings in the CareQOL app

During the 10-day run-in period between the baseline visit and the start of the intervention, study team members will assist participants to make sure that participants can:

- Successfully wear and sync the Fitbit®
- Successfully respond to the EMA prompts

Participants who are unable to successfully complete the run-in period will be terminated from the study and noted as a screen failure.

Training and training materials will be provided to all study team members. New study members will undergo training before the study is started. Training will be documented in the electronic regulatory binder.

Participant adherence to the protocol will be assessed throughout the study. Study staff will have access to the CareQOL app dashboard which can be used to monitor participant engagement and adherence with the app. Specifically, study staff will monitor:

- Adherence to EMA entry
- Adherence to Fitbit® use/syncing
- Adherence to completing the end of month surveys (~30, 60, 90 day)

Adherence will be calculated as a percentage for each of these areas for all participants who are not withdrawn or lost to follow-up.

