## 7 STUDY INTERVENTION/EXPERIMENTAL MANIPULATION DISCONTINUATION AND PARTICIPANT DISCONTINUATION/WITHDRAWAL

### 7.1 PARTICIPANT DISCONTINUATION/WITHDRAWAL FROM THE STUDY

Participants are free to withdraw from participation in the study at any time upon request.

An investigator may discontinue a participant from the study for the following reasons:

- Lost-to-follow up; unable to contact participant (see **Section 7.2, Lost to Follow-Up**)
- Any event or medical condition/situation that occurs that would indicate that continued collection of follow-up study data would not be in the best interest of the participant or might require treatment that would confound the interpretation of the study
- The participant meets an exclusion criterion (either newly developed or not previously recognized) that precludes further study participation
- The participant is non-compliant with the study protocol

The reason for participant discontinuation or withdrawal from the study will be recorded. Participants who provide informed consent and are randomized but do not complete the 10-day run-in period will be replaced. Participants who withdraw or are discontinued before the end of the 3-month (~90 day) home monitoring period will be replaced.

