## 7.2 LOST TO FOLLOW-UP

A participant will be considered lost to follow-up if: 1) he or she does not complete the end of month survey at the end of the 3-month (~90 day) home monitoring period **and** 2) study staff are unable to contact the participant after a minimum of 3 attempts.

The following actions must be taken if a participant fails to complete the end of the month survey at the end of the 3-month (~90 day) intervention period:

- The site will attempt to contact the participant and counsel the participant on the importance of completing the survey and ascertain if the participant wishes to and/or should continue in the study.
- The site will make every effort to regain contact with the participant (where possible, 3 telephone calls/emails/texts and, if necessary, a certified letter to the participant's last known mailing address or local equivalent methods) before a participant is deemed lost to follow-up. These contact attempts will be documented in the participant's study file.
- Participants that continue to be unreachable will be considered to have withdrawn from the study (with a primary reason recorded as lost to follow-up).

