#### Secondary Endpoints:

- 2) We hypothesize that this intensive data collection protocol will be both feasible and acceptable for care partners (regardless of group assignment)
  - a. Attrition as measured by the percent of participants completing the study (i.e., we expect  $\geq 80\%$  of participants to complete the study)
  - b. Percent missing data of total expected data for each person and on average will also be calculated to characterize the feasibility of this data collection method (i.e., we expect  $\leq 60\%$  missing data for the daily assessment questions and  $\geq 80\%$  completion rates for the three monthly surveys)

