## 9.3 POPULATIONS FOR ANALYSES

The primary endpoint will examine survey responses on the feasibility and acceptability questionnaire that is designed to evaluate our intensive data collection protocol in the full sample (i.e., N=60 care partners). Secondary endpoints will include attrition and adherence estimates (again across the full sample). Exploratory analyses will be conducted to identify trends for an improvement in HRQOL scores (i.e., strain, depression, and anxiety) for care partners that are randomized to the intervention group. These analyses will also look for a trend for an improvement in the remaining HRQOL scores for care partners that are randomized to the intervention group, and will compare the JITAI group with the control group on all of the different HRQOL measures. Exploratory analyses may also compare important subgroups (e.g., caregiver groups that differ by diagnosis [SCI, HD or HCT], relationship type [parent vs. spousal caregivers], caregiver groups that differ by sex [male vs. female caregivers], caregiver groups that differ according to the functional status of the person with TBI (e.g., complicated mild vs. moderate vs. severe TBI or perceived functional status based on Mayo Portland Adaptability Index scores). Exploratory analyses will be an intention-to-treat approach where the participant will contribute data to the arm he/she was randomized to regardless of the amount of data contributed (i.e. the duration of participation).

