#### 9.4.3 ANALYSIS OF THE SECONDARY ENDPOINT(S)

##### Secondary Endpoints:

- Attrition (% of participants completing the final assessment—the assessment that is given at the end of month 3)
- Adherence (% missing data of total expected data for each person)

Attrition will be reported as the number of participants that complete the final assessment out of the total of number of study participants that completed the baseline assessment. In addition, the total number of days that participants completed EMA assessments, the monthly surveys, and the number of participants that complete the study will be calculated. Descriptive statistics will be calculated for missing data across the study period and by moment/day.

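### Section 6.2 leaves withdrawn and lost participants out of adherence, against the full sample in 9.3, and 9.4.3 does not say which data are expected after withdrawal

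*Combined protocol and SAP*

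**What the plan says.** Section 6.2 (Fidelity) lists three things that staff monitor: EMA entry, Fitbit use and syncing, and the surveys at about days 30, 60 and 90. It then says: "Adherence will be calculated as a percentage for each of these areas for all participants who are not withdrawn or lost to follow-up".

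The statistical sections read differently. Section 9.3: "Secondary endpoints will include attrition and adherence estimates (again across the full sample". Section 9.4.3 defines the endpoint as "Adherence (% missing data of total expected data for each person". Section 9.1 attaches expected levels: no more than 60% missing for the daily questions, and 80% or more for "completion rates for the three monthly surveys". It sets no level for Fitbit data.

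Section 7 determines who is withdrawn or lost. Among the reasons in 7.1 for which an investigator may discontinue someone is: "The participant is non-compliant with the study protocol". The same section adds: "Participants who withdraw or are discontinued before the end of the 3-month (~90 day) home monitoring period will be replaced". Section 7.2 calls a participant lost when two conditions both hold: "he or she does not complete the end of month survey at the end of the 3-month (~90 day) home monitoring period", and "study staff are unable to contact the participant after a minimum of 3 attempts".

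The primary questionnaire is given at day 90 only (8.1.5.3, 9.4.2). Section 9.1 sets 80% agreement, 9.3 names the full sample of 60, and 9.4.2 plans item counts and descriptive statistics. None of them says how a participant without a questionnaire is counted.

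**The concern.** Once anyone leaves, 6.2 and 9.3 can give different adherence figures, and the text does not say which one is the endpoint. The people whom 6.2 drops plausibly include many who found the protocol hardest to sustain, so the figure that remains is likely to be too favourable.

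Part of this is built in. A missed day-90 survey together with failed contact makes a person lost under 7.2, and 6.2 then removes that person from the survey-adherence percentage. Discontinuation for non-compliance under 7.1 is a second possible route.

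Feasibility is the primary question, and 9.2 says that the results are to inform a larger trial. An adherence rate that holds only for those who stayed would mislead that trial about how much data to expect.

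**Working it through.** **The plan's own figures.** Sections 9.2 and 9.3 use N = 60, which agrees with 3 groups × 20 and 2 arms × 30. The 60–90 in 1.1 and 4.1 agrees with 3 × 2 × 10 and 3 × 2 × 15. The levels in 9.1 have no calculation behind them to reproduce.

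**Inputs.** From the documents: 90 daily assessments and 3 monthly surveys per person; levels of 60% missing and 80% completed (9.1); at least 80% of participants expected to complete, so 20% leaving is the most that 9.1 tolerates. Assumed: when people leave, and how well stayers adhere.

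**Monthly surveys.** Assume that 60 enter home monitoring, 12 leave after the first survey, and the 48 stayers return 130 of 48 × 3 = 144.

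- Section 6.2, stayers only: 130/144 = 90%.
- Everyone, surveys after leaving not expected: (130 + 12)/(144 + 12) = 142/156 = 91%. Averaging person-level percentages instead gives (130/3 + 12)/60 = 92%.
- Everyone, three surveys expected of each: 142/180 = 79%, below the 80% level.

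Write c for the stayers' completion rate. With 20% leaving after the first survey, the last reading gives 0.8c + 0.2 × (1/3), which equals 0.80 at c = 0.917. So 6.2 and the last reading disagree about the 80% level when stayers complete from 80% to just under 92%. With 10% leaving, 0.9c + 0.1 × (1/3) = 0.80 at c = 0.852, and they disagree only between 80% and about 85%.

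**Daily EMA.** Write x for the stayers' missing share. Assume that 20% stop at day 30, having answered at the stayers' rate until then. With all 90 days expected, overall missing = 0.8x + 0.2 × (30x/90 + 60/90) = 0.867x + 0.133.

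- x = 0.55 gives 61%.
- x = 0.30 gives 39%, well inside the level.
- The 60% level is crossed at x = 0.538. For a stop at day 15 the crossing is at 0.520, and for day 60 at 0.571.

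If later days are not expected, the missing share stays at x.

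**Primary questionnaire.** At 80% completion of 60 there are 48 respondents. The smallest passing count among respondents is 39/48 = 81%. Over all 60, the same 39 give 39/60 = 65% if no non-responder agrees, and (39 + 12)/60 = 85% if all would. If non-responders counted as not agreeing, 80% of 60 = 48, so all 48 respondents would have to agree.

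**The case against.** The strongest defence is that 6.2 is a fidelity section about staff watching a dashboard, while endpoints belong to section 9. That would settle the matter if the text said so. But 6.2 says that a percentage will be calculated, and it names EMA entry and monthly surveys, the two quantities with levels in 9.1.

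Second, full sample in 9.3 may mean both arms and all diagnoses pooled, because 9.1 speaks of care partners regardless of group and 9.3 contrasts the full sample with comparisons by arm and subgroup. This reading is fair. It softens the clash, but it leaves 6.2 as a stated exclusion that section 9 does not mention.

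Third, the fall to 79% does not come from the exclusion alone. Adding leavers without their later surveys raises the figure to 91%. This is correct, and it is why the two definitions must be fixed together.

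Fourth, losses would remain visible: 9.4.3 reports attrition separately and missing data by day, and the levels in 9.1 are worded as expectations. This limits the harm but does not fix the adherence denominator.

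Fifth, the EMA level may never bind. The intern study in 2.2 had 92% of participants giving data on at least 80% of days.

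A reader might infer that 6.2 removes every low adherer. The documents do not support that. Someone who misses the day-90 survey but can be reached, and does not withdraw, stays in. How often non-compliance leads to discontinuation is unknown, since 10.1.7 does not even report missed assessments as deviations.

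**Conclusion.** The point holds for adherence. Section 6.2 states an exclusion that does not fit 9.3, and 9.4.3 leaves expected data after withdrawal undefined. If 6.2 is followed, the result describes those who stayed. Under the assumed 20% loss after the first survey, survey completion is 90%, 91% or 79% depending on the rule, so the choice can decide whether the 80% level is met. For EMA with a day-30 stop, the verdict changes only if stayers already miss about 54–60%. With no dropout the definitions coincide. The timing and amount of dropout are assumptions, with 20% the limit implied by 9.1.

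Three stronger readings go too far:

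- A reader might infer that the primary 80% level must count non-responders as not agreeing. The documents do not say this. The missing rule is an omission, and requiring 48 of 48 respondents to agree is hard to square with a plan that also accepts 80% completion.
- A reader might infer that 9.4.3 wrongly handles run-in failures in attrition. Its denominator is baseline completers, and run-in follows baseline, which points to including them. The screen-failure wording in 5.4 and 6.2 points the other way. It needs a clarifying sentence.
- A reader might take N = 60 against 60–90 as a design error. The amendment history gives over-recruitment for missing data as the reason for the range, so 60 may mean the number analysable.

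**What to change.** 1. In 6.2, delete the restriction to participants who remain, or label that figure as completers-only monitoring. In 9.4.3, compute endpoint adherence for everyone who enters home monitoring, including those later withdrawn, lost, discontinued or replaced. Count 90 daily assessments and 3 monthly surveys as expected for each, and show the completers-only figure beside it.
2. In 9.4.2, report each questionnaire item among respondents, with the number not responding. Also show agreeing respondents over all who entered home monitoring, as a descriptive lower bound. The sponsor should state in advance which denominator the 80% level uses.
3. As clarifications, say whether run-in failures (5.4, 6.2) stay in the 9.4.3 attrition denominator, and align N = 60 in 9.2 and 9.3 with 60–90 in 1.1 and 4.1.

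The cost is wording and an extra column in the feasibility tables. No further participants, visits or data are needed, since 10.1.3 already retains data from those who withdraw. The downside is that adherence percentages become somewhat less favourable, and the lower bound for the primary partly repeats attrition.

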### 6.3 CONCOMITANT THERAPY

There are no concomitant treatment or management strategy restrictions for this study. Information about current treatments (medications and non-medications) will be collected at baseline. Changes in treatments will be captured at the end of month 3 (~90 days) during the home monitoring period.

## 7 STUDY INTERVENTION/EXPERIMENTAL MANIPULATION DISCONTINUATION AND PARTICIPANT DISCONTINUATION/WITHDRAWAL

### 7.1 PARTICIPANT DISCONTINUATION/WITHDRAWAL FROM THE STUDY

Participants are free to withdraw from participation in the study at any time upon request.

An investigator may discontinue a participant from the study for the following reasons:

- Lost-to-follow up; unable to contact participant (see **Section 7.2, Lost to Follow-Up**)
- Any event or medical condition/situation that occurs that would indicate that continued collection of follow-up study data would not be in the best interest of the participant or might require treatment that would confound the interpretation of the study
- The participant meets an exclusion criterion (either newly developed or not previously recognized) that precludes further study participation
- The participant is non-compliant with the study protocol

The reason for participant discontinuation or withdrawal from the study will be recorded. Participants who provide informed consent and are randomized but do not complete the 10-day run-in period will be replaced. Participants who withdraw or are discontinued before the end of the 3-month (~90 day) home monitoring period will be replaced.

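### Section 7.1 provides only for leaving the study, so formal leavers have no Day-90 score for the comparison that 9.3 calls intention-to-treat

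*Combined protocol and SAP*

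**What the plan says.** The heading of section 7 names two events: "STUDY INTERVENTION/EXPERIMENTAL MANIPULATION DISCONTINUATION AND PARTICIPANT DISCONTINUATION/WITHDRAWAL". Its subsections are 7.1, on leaving the study, and 7.2, on loss to follow-up. Neither describes someone who stops the intervention but is still followed.

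In 7.1 both routes lead out of the study:

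- For participants: "Participants are free to withdraw from participation in the study at any time upon request".
- For investigators: "An investigator may discontinue a participant from the study for the following reasons". The reasons include "The participant is non-compliant with the study protocol" and a condition or situation that "might require treatment that would confound the interpretation of the study".

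Then: "Participants who withdraw or are discontinued before the end of the 3-month (~90 day) home monitoring period will be replaced". Section 10.1.3 keeps data already given by people who withdraw, but no section provides for collecting more from them.

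Section 3 defines the exploratory endpoints as change from baseline in strain, depression and anxiety at the end of the 90 days. Section 9.3 compares the arms on all HRQOL measures and says: "Exploratory analyses will be an intention-to-treat approach where the participant will contribute data to the arm he/she was randomized to". It adds that this holds however long the person took part and however little they supplied. Section 9.4.1 gives a two-group t-test, or a nonparametric test if the data are not normal. No method for missing scores is named.

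**The concern.** Keeping a leaver in the assigned arm does not supply a Day-90 change score, and the planned test cannot use a person without one. In practice the comparison rests on those who reached Day 90. Enrolling a substitute restores the count, but the substitute's score says nothing about how the person who left would have fared.

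The loss need not be alike in the two arms. The Fitbit, the daily questions and the monthly surveys are common to both, but only the JITAI arm receives messages, so only that arm can leave because of them. Two of the investigator's grounds, non-compliance and potentially confounding treatment, also arise after randomisation and may be related to how the person is doing.

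Section 9.2 says the study is meant to give a point estimate of the JITAI effect for a larger trial, so a shift in that estimate would carry into the next trial's planning. The same people also miss the feasibility questionnaire, which is given only at Day 90, but the figures below concern only the HRQOL comparison.

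**Working it through.** **Inputs from the plan**

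- Randomised per arm: 30 (9.2, N = 60), up to 45 (4.1, N = 90). Check: 3 × 20 = 2 × 30 = 60, and 3 × 30 = 2 × 45 = 90.
- Completion: at least 80% expected (9.1), so the largest loss the plan expects is L = 0.20.
- Scale: T metric with SD 10 (8.1.5). The SD of change is not given.

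The plan states no figure for bias or for missing Day-90 scores, so there is none to reproduce.

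**Assumptions of this review**

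- d is the number of T points by which leavers would have changed less favourably than stayers: 3, 5 or 8.
- r is the share of leavers who would still answer the surveys if asked: 0.5, taken to be typical of all leavers.

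**Scores that could be missing.** 0.20 × 30 = 6 and 0.20 × 45 = 9 per arm. These are upper figures. They include people who cannot be reached, whom 7.2 already pursues, as well as formal leavers.

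**Bias in the arm difference when only stayers are scored**

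Bias = L(JITAI) × d(JITAI) − L(control) × d(control)

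- Equal attrition and equal gaps, for example 0.20 × 5 − 0.20 × 5 = 0.
- Only JITAI leavers differ (control gap zero): 0.20 × 3 = 0.6, 0.20 × 5 = 1.0, 0.20 × 8 = 1.6, each in favour of JITAI.

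**After the fix, in the one-sided case**

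Bias = L × d − (L × r × d) / (0.8 + L × r). With L = 0.20 and r = 0.5, the denominator is 0.8 + 0.1 = 0.9.

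| Gap d | No further surveys | Half of leavers surveyed |
|---|---|---|
| 3 | 0.60 | 0.60 − 0.30/0.9 = 0.27 |
| 5 | 1.00 | 1.00 − 0.50/0.9 = 0.44 |
| 8 | 1.60 | 1.60 − 0.80/0.9 = 0.71 |

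The share of randomised people with a Day-90 score rises from 80% to 90%.

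**Scale against chance error.** Taking SD 10 for change (an assumption), the standard error of the arm difference is 10 × √(2/n): 2.9 with 24 scored per arm (80% of 30) and 2.4 with 36 (80% of 45). A shift of 0.6 to 1.6 points lies below one standard error.

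**The case against.** A reader might infer that outcome collection ends whenever the intervention does, so that anyone tired of the messages, the Fitbit or the daily prompts must leave. The documents do not support that. Participants may skip daily assessments and are told to take the Fitbit off if it irritates the skin (2.3.1). They may choose not to engage with notifications (6.1). Missed daily entries and Fitbit data are expected and are not reported as deviations (10.1.7). Monthly surveys can be answered in the app or by interview (8.1.5.3). Someone can therefore drop much of the daily protocol and still give every monthly score. The gap covers only those who formally withdraw or are discontinued.

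Other objections stand in part:

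- Section 7.2 already requires contact when the Day-90 survey is missed. It does not say that this covers people who have already withdrawn or been discontinued.
- Section 9.3 defines its own intention-to-treat approach and does not promise a Day-90 score for everyone. That is so, but the Day-90 comparison still lacks those scores.
- Removal for non-compliance is discretionary, so how often it happens is unknown.
- The comparison is exploratory and looks for trends, and the exploratory hypotheses in 9.1 concern change within the JITAI arm. This limits the weight of the point. It does not remove it, because the within-arm change loses the same scores and has no control arm to offset them.
- A reader might take 1.0 T point as the expected bias. It is not: 20% is the most loss the plan expects, the gap and the 50% response are assumed, and matching losses in controls bring the bias to zero.
- The consent form and the manual of procedures are not available here, and either may offer partial withdrawal.

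**Conclusion.** The point holds for participants who formally withdraw or whom an investigator discontinues. They are replaced, the plan provides for no further surveys from them, and the comparison in 9.3 then lacks their Day-90 change.

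At the 80% minimum, up to 6 to 9 of 30 to 45 per arm could lack that score. The bias runs from zero, with equal attrition and equal gaps in both arms, to about 0.6 to 1.6 T points in favour of JITAI, if only JITAI leavers differ and do so by an assumed 3 to 8 points. The documents do not show where in that range the trial would fall.

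The effect is modest beside chance error and touches an exploratory comparison. It is still worth correcting, because the surveys already exist, are short and remote, and do not depend on the daily protocol.

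**What to change.** Leave unchanged when and why anyone stops. Then:

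- **7.1:** separate *stopped the daily protocol* (messages, daily questions, Fitbit) from *withdrew from the study*. Keep offering the scheduled Day-30, 60 and 90 surveys, by app or interview, to everyone randomised who stops early, unless the person declines or the investigator judges that further data collection is not in their interest.
- **7.2:** say that the contact steps apply to these people too.
- **9.3:** say that their scores are analysed in the randomised arm, even if they have been replaced.
- **9.4.3:** say that they still count as non-completers for the 80% attrition endpoint. Completion is now defined by the final assessment, so without this change an early stopper who answers at Day 90 would raise the completion figure.
- **6.2:** say how they enter the adherence denominator, which now leaves out only those withdrawn or lost to follow-up.
- **Reporting:** give both categories by arm. This would also show whether people reject the messages or the whole study.

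The cost is a short amendment and a sentence in the consent form. The surveys, the $10 payment for each and the contact procedure are already in place. The downside is some extra contact with people who stopped early.
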